9.13 Exploratory Analyses

Pharmacokinetics/Pharmacodynamics

The relationship between GSK1265744 PK parameters and demography variables (age, gender, race, ethnicity, weight, BMI, smoking status) or PD endpoints (conversion to HIV-infected status, safety parameters) may be explored.

Pharmacogenomics Analysis

Specific genes may be studied that encode the drug targets, drug mechanism of action pathways, drug metabolizing enzymes, or drug transporters or which may underpin AEs, disease risk, or pharmacokinetics or drug response. These candidate genes may include a common set of absorption, distribution, metabolism, and excretion genes that are studied to determine the relationship between gene variants and pharmacokinetics or safety parameters. In addition, future research may identify other enzymes, transporters, proteins, or receptors that may be involved in response to GSK1265744. The genes that may code for these proteins may also be studied.

A detailed statistical analysis plan will be documented separately once the pharmacogenomics study plan is finalized.

10 SMC REPORTS

10.1 Cohort data will be analyzed and presented separately in all SMC report periods. If appropriate, they will be analyzed jointly in the last SMC report period. Study Conduct Report (SMC Open Report)

10.1.1 List of Tables

- Accrual summary by site and by gender
- Accrual summary and accrual by calendar month and by site
- Specimen collection by pre-specified specimen collection visits and site
- Retention by study visit and by site
- Baseline demographics for total and by site
- Completion of behavioral assessment questionnaire (BQ) by study visit and site
- Completion of Study Medication Satisfaction questionnaire (SMSQ) by study visit and site
- Completion of Baseline Acceptability questionnaire (BAQ) by site and completion of Follow-up Acceptability questionnaire (FAQ) by study visit and site
- Adherence as measured by pill counts during 4 weeks of oral phase by study visit (Weeks 2 and 4) and site

- Adherence as measured by self-report at Week 4 by site
- Completion of injections by study visit and site
- Baseline sexual risk behavior
- Study product holds and earlier discontinuations by site
- Reasons for early discontinuation of study regimen during the oral phase by site
- Reasons for not advancing to injection phase by site
- Reasons for early discontinuation of study regimen during the injection phase by site
- Social harms/impacts summary
- Pregnancy listing

10.1.2 List of Graphs

- Accrual graph by calendar month – total
- Accrual graph by calendar month - by site

10.2 Safety Tables and Graphs (SMC Close Report)

10.2.1 List of Tables

- Permanent discontinuation of study regimen during the oral phase (Weeks 0-5) by treatment arm
- Permanent discontinuation of study regimen during the injection phase (Weeks 5-41) by treatment arm
- Permanent discontinuation of study regimen during the tail phase (Weeks 41-105/109) by treatment arm
- List of early discontinuation of study regimen (reason, study week)
- Grade 3 or higher adverse events by treatment arm during the oral phase (Weeks 0-5)
- Proportion of Grade 2 or higher adverse events by treatment arm during the oral phase (Weeks 0-5)
- Adverse events by severity and relationship to study product during the oral phase (Weeks 0-5)

- Adverse events by MedDRA preferred term ordered by system organ class during the oral phase by treatment arm (Weeks 0-5)
- listing of Grade 3 or above adverse events during the oral phase by treatment arm (Weeks 0-5) with details of the events including severity, relationship to the study product, on-set date, outcome, duration, the enrollment date and days since the enrollment.
- Grade 1 or above AST/ALT by treatment arm during the oral phase (Weeks 0-5)
- Grade 2 or higher adverse events by treatment arm during the injection phase (Weeks 5-41)
- Number and percentage of adverse events by severity and relationship to study product during the injection phase (Weeks 5-41)
- Adverse events by MedDRA preferred term ordered by system organ class during the injection phase (Weeks 5-41)
- Injection site reaction (ISR) adverse events during the injection phase by BMI (above/below median BMI) (Weeks 5-41)
- Grade 1 or above AST/ALT by treatment arm during the injection phase (Weeks 5-41)
- Adverse events by MedDRA preferred term ordered by system organ class during the injection phase (Weeks 5-105/109)
- listing of Grade 3 or above adverse events during the whole injection phase (Weeks 5-81) with details of the events including severity, relationship to the study product, on-set date, outcome, duration, last injection date, and the number of injections prior to the event
- Adverse events by severity and relationship to study product and treatment arm during the whole injection phase (Weeks 5-105/109)
- Grade 1 or above AST/ALT by treatment arm during the whole injection phase (Weeks 5-105/109)
- HIV infection status by study arm
-

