3.2 Secondary Objectives and Endpoints

Secondary Objectives

- Evaluate the safety and tolerability of GSK1265744 (daily oral 744 + 744LA) for 76 weeks of follow-up after final injection (each cohort will be analyzed separately)
- Evaluate the safety and tolerability of oral 744 from Week 0 to Week 5

- Evaluate the pharmacokinetics of 744LA administered as 800 mg IM every 12 weeks for 52 weeks of follow-up after final injection
- Evaluate differential pharmacokinetics of 744LA in participants by age, gender, race, ethnicity, weight, body mass index (BMI), and smoking status
- Evaluate the acceptability of 744LA injections
- Evaluate the effect of 744LA on sexual risk behavior by change from enrollment for repeat assessments to during the study period
- Evaluate HIV incidence and antiretroviral drug resistance, if any participants acquire HIV infection during the study
- Evaluate the safety, tolerability and pharmacokinetics of 744LA in the subset of women who use a hormone-based contraceptive

Secondary Endpoints

- Proportion of participants who discontinue either oral or injectable study product for reasons of toxicity, tolerability, or acceptability prior to completion of the full oral and injectable phases
- Proportion of participants experiencing Grade 2 or higher clinical AEs and laboratory abnormalities during 52 weeks following final injection (safety) and any AE that leads to discontinuation (tolerability) during the aggregate oral and injectable phases
- Proportion of participants experiencing Grade 2 or higher clinical AEs and laboratory abnormalities (safety) and any AE that leads to discontinuation (tolerability) in the oral phase and washout period
- Plasma drug levels of GSK1265744 at designated time points after each injection of 744LA (by cohort only)
- Plasma drug levels of GSK1265744 at designated time points after each injection of 744LA stratified by age, gender, race, ethnicity, weight, BMI, and smoking status
- Proportion of participants willing to use an injectable agent such as the study product for HIV prevention in the future
- Change from enrolment of self-reported sexual behaviour (number of sexual partners, episodes of unprotected anal and/or vaginal intercourse) during the study period using a standardized assessment tool (in aggregate only)
- Number of incident HIV infections through the study period, including number with treatment emergent resistance

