4.3 Study Duration

Approximately 3 years. Accrual will require approximately 16 to 24 weeks (4 – 6 months) for each cohort. Study participants in both cohorts will receive oral tablets for 4 weeks, followed by a 1 week wash out period. Cohort 1 will then receive intra-muscular injections at 3 time points over 24 weeks (6 months); cohort 2 will receive intra-muscular injections at five time points over 28 weeks (7 months). Participants in the active study product arm will be followed for 76 weeks (18 months) after their last injection. Participants in the placebo arm will be followed until 76 weeks after their last injection or until the last participant in the active study product arm in cohort 2 completes their Week 41 visit, whichever comes first, at which time the study will be unblinded to assess the primary endpoint. When all procedures related to unblinding are completed, participants in the placebo arm will no longer be followed.

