4.8 Blinding

Study site staff, with the exception of the site Pharmacist of Record or their designee, and participants will be blinded to the random assignments. Blinding will be maintained until the last participant enrolled in to the active drug arm in cohort 2 has completed their Week 41 visit (the time point of the primary endpoint of the study), and when all data related to the Week 41 visit has been entered into the database, as well as cleaned and verified. At a specified time directed by the HPTN SDMC, participants will be unblinded to their treatment assignment, and participants in the placebo arm will no longer need to be followed. Participants in the active study product arm will continued to be followed for 52 weeks after their last injection.

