9.5.5 Safety Endpoint

Primary safety endpoint is the proportion of participants experiencing any Grade 2 or higher clinical AEs or laboratory abnormalities since the initial injection to 12 weeks (8 weeks) after the last injection in Cohort 1 (Cohort 2) among the participants who complete at least one injection to evaluate the safety of the 744 injectable during the injection phase. A secondary safety endpoint is the proportion of Grade 2 or higher clinical AEs or laboratory abnormalities occurred from the initial injection to 76 weeks in both cohorts after last injection among the participants who complete at least one injection to evaluate the safety of the 744 injectable in long term; the proportion of Grade 2 or higher AEs or laboratory abnormalities occurred during the oral phase (Weeks 0-5) among all enrolled participants to evaluate the safety of the oral 744 product; and the proportion of Grade 2 or higher AEs or laboratory abnormalities occurred during the whole study period among the all enrolled participants to evaluate the safety of the oral and injectable product. The proportions of endpoints and the %95 confidence intervals will be estimated for each treatment arm. The 95% CIs will be estimated using Wilson score method¹. The proportions of endpoints will be compared between the treatment arms using Fisher Exact test.

In addition, the safety endpoint rate might be calculated for each treatment arm and compared between the treatment arms. The safety endpoint rate is the number of the participants who have experienced Grade 2 or higher clinical AEs or laboratory abnormalities during the study period (defined in each safety analysis) divided by the person-time-at-risk throughout the observation period within the study period.

The 95% exact confidence interval of the safety event rate will be calculated for each treatment arm, assuming the rate follows the Poisson distribution. The safety event rate will be compared between the treatment arms using exact Poisson test.

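### A 52-week horizon survives in three places of a SAP otherwise built on 76 weeks: it truncates one SMC Grade 3+ listing, gives a secondary safety endpoint two windows, and contradicts the stated follow-up

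*SAP*

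**What the plan says.** Section 1 states that the SAP was modified to extend the tail visits under Letter of Amendment #3. The longer horizon appears in the secondary safety objective (Section 3.2), in Section 4.3 ("Participants in the active study product arm will be followed for 76 weeks (18 months) after their last injection"), in the visit schedule (Section 4.4, final visits at Weeks 105 and 109), in the tail-phase definition (Section 7.1) and in Section 9.5.5.

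Three places differ.

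1. **Closed SMC report, Section 10.2.1.** One item is a "listing of Grade 3 or above adverse events during the whole injection phase (Weeks 5-81"). Another item in the same list reads "Adverse events by severity and relationship to study product and treatment arm during the whole injection phase (Weeks 5-105/109"), and the AST/ALT table uses the same label and the same longer range. Section 7.1 does not define that label, so only the bracketed weeks give it a meaning.
2. **Secondary safety endpoint.** Section 3.2: "Proportion of participants experiencing Grade 2 or higher clinical AEs and laboratory abnormalities during 52 weeks following final injection (safety"). Section 9.5.5 counts events that "occurred from the initial injection to 76 weeks in both cohorts after last injection".
3. **Follow-up of the active arm.** Section 4.8 says that these participants "will continued to be followed for 52 weeks after their last injection", against the 76 weeks in Section 4.3.

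**The concern.** All of these statements are current text; none comes from a change log. A programmer who follows them literally produces outputs that do not cover the same period.

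The listing matters because it is the closed-report item that gives, for each Grade 3+ event after the first injection, severity, relationship, onset, outcome, duration, last injection date and number of prior injections. Stopping it at Week 81 removes that detail for the end of a tail that the SAP says it was modified to extend. Section 5.1 has the SMC reviewing data at least every six months.

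The endpoint matters because one secondary safety proportion would be defined over two different periods, and its value would depend on which section was programmed.

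The conflict between Sections 4.3 and 4.8 lies underneath both, since the analysis windows depend on how long participants are followed.

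**Working it through.** **Inputs.** Section 4.4: first injection at Week 5 in both cohorts; last injection at Week 29 (Cohort 1) and Week 33 (Cohort 2); tail visits at Weeks 53, 65, 77, 89 and 101; final visits at Weeks 105 and 109. Horizons: 76 weeks (Sections 4.3 and 9.5.5) and 52 weeks (Sections 3.2 and 4.8). Listing end: Week 81 (Section 10.2.1). The arithmetic is for a participant who receives the full injection course on schedule.

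**Step 1: reproduce the plan's own end weeks.** Last injection + 76: 29 + 76 = 105 and 33 + 76 = 109. Both equal the final visits in Section 4.4, so the schedule is built on 76 weeks.

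**Step 2: where Week 81 fits.** Last injection + 52: 29 + 52 = 81 and 33 + 52 = 85. Week 81 is the 52-week point for Cohort 1 only. In Cohort 2 it falls 81 − 33 = 48 weeks after the last injection, so it matches neither horizon. Section 10.1 has the cohorts presented separately in SMC reports, yet the listing has a single end week.

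**Step 3: what the listing omits.**

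| | Cohort 1 | Cohort 2 |
|---|---|---|
| Weeks omitted | 105 − 81 = 24 | 109 − 81 = 28 |
| Share of the 76 weeks after the last injection | 24/76 = 32% | 28/76 = 37% |
| Share of the tail phase from Week 41 (Section 7.1) | 24/64 = 37.5% | 28/68 = 41% |
| Share of observation from Week 5 | 24/100 = 24% | 28/104 = 27% |
| Scheduled visits omitted | 89, 101, 105 | 89, 101, 109 |

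**Step 4: the two endpoint windows.** This takes Section 3.2 literally, with the safety part counted over the 52 weeks following the final injection.

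| | Section 3.2 | Section 9.5.5 |
|---|---|---|
| Cohort 1 | Weeks 29 to 81 (52 weeks) | Weeks 5 to 105 (100 weeks) |
| Cohort 2 | Weeks 33 to 85 (52 weeks) | Weeks 5 to 109 (104 weeks) |

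The ends differ by 24 weeks in each cohort. The starts differ by 29 − 5 = 24 weeks in Cohort 1 and 33 − 5 = 28 weeks in Cohort 2. Changing 52 to 76 in Section 3.2 would align the ends but leave the starts apart. Final report Table 19 does not settle the matter: its oral, injection, tail and on-treatment periods coincide with neither window.

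**The case against.** **Late severe events are still reported.** A reader might infer that Grade 3+ events after Week 81 disappear from reporting. They do not. The same closed SMC report tabulates adverse events by severity, relationship and arm, and by MedDRA term, over Weeks 5-105/109. Final report Tables 9, 10, 11 and 19 cover the tail, and Table 18 lists expedited and serious events individually. This stands. The loss is confined to the event-level SMC listing, and it bites on Grade 3+ events that are neither expedited nor serious.

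**Late Cohort 2 events may fall after unblinding.** Unblinding follows the last Cohort 2 active participant's Week 41 visit and data cleaning (Sections 4.3 and 4.8). With 16 to 24 weeks of accrual, the first Cohort 2 participant is then at about Week 41 + 16 = 57 to 41 + 24 = 65. Unless cleaning takes more than about 81 − 65 = 16 weeks, Cohort 2 events after Week 81 occur once the study is unblinded and placebo follow-up is ending. This reduces the value of the listing for comparing arms late in Cohort 2. It does not justify a cut-off that disagrees with the sibling tables.

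**Section 9.5.5 is the operative analysis text.** It agrees with the safety objective, Sections 4.3 and 4.4, and the tail definition, so a careful programmer would probably follow it. That lowers the practical risk, but the formal endpoint definition in Section 3.2 still says something else.

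**The earlier horizon is not stated.** Section 1 mentions the extension without naming the previous length. That the 52-week statements are leftovers is a reasonable inference, not a quoted fact. The contradiction does not depend on it.

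**The PK objective.** Section 3.2 also gives 52 weeks for pharmacokinetics ("Evaluate the pharmacokinetics of 744LA administered as 800 mg IM every 12 weeks for 52 weeks of follow-up after final injection"), and a reader might count this as a fourth leftover. Nothing in the SAP shows that it is one: PK follow-up may legitimately be shorter than safety follow-up. It is not part of this point.

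**Conclusion.** The inconsistency is real and sits in three places. The SMC Grade 3+ listing ends 24 weeks (Cohort 1) or 28 weeks (Cohort 2) before the end of scheduled follow-up, and its end week fits Cohort 2 under neither horizon. The secondary long-term safety endpoint has two windows that differ at both ends. Sections 4.3 and 4.8 contradict each other on how long the active arm is followed.

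The consequence is bounded. One event-level monitoring listing and one secondary proportion are affected; aggregate safety reporting and the primary endpoint are not. How far the secondary proportion would change cannot be computed from the SAP, because it gives no event rates by period.

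The week counts assume full-course participants on the nominal schedule, and the endpoint comparison assumes the literal reading of Section 3.2. The point merits correction before the outputs are programmed.

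**What to change.** - Reconcile Sections 4.3 and 4.8 so that the SAP states one follow-up duration for the active arm. The analysis windows should then follow from it.
- In Section 10.2.1, run the Grade 3+ listing over Weeks 5-105/109, as its sibling tables do, with the end week stated by cohort. Define the phase label once, in Section 7.1.
- Give the long-term safety endpoint one start and one end, in identical terms in Sections 3.2 and 9.5.5, and name the final report table that presents it.
- Leave the PK objective out of this correction.

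The cost is SAP wording and matching table shells. The Week 89, 101 and final visits are already in the Section 4.4 schedule, so no visits need to be added to it.

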10.2.2 List of Graphs

- Kaplan-Meier curves of time to permanent discontinuation by treatment arm (For those who complete the study and currently stay in the study, their time to permanent discontinuation will be censored at the last visit date)
- Box plots of maximum liver chemistries (AST, ALT, ALP, and bilirubin) by treatment arm and visit during oral, injection, and oral+injection phase.

- Scatter plots of maximum liver chemistries during oral, injection, and oral+injection phase vs. baseline.
- Matrix plot of maximum of liver chemistries during the oral, the injection, and the oral+injection phase.
- Shift plot of some laboratory measure at each visit week vs. baseline during the oral, injection, and oral+injection phase.
- Cumulative incidence curve of the time to first occurrence of grade 1 or greater elevation in ALT/AST will be generated by treatment arm during the oral, injection and oral+injection phase.

11 FINAL STUDY REPORT (FSR)

The data will be analyzed by cohort and in aggregate (if it is appropriate).

11.1 Study Population Summary

All study population characteristics will be provided for table and by treatment arm

11.1.1 Lists of Tables

- Table 1 Summary of study populations
- Table 2 Summary of subject accountability: Study conclusion record
- Table 3 Summary of baseline demographic characteristics
- Table 4 Summary of baseline risk behavior
- Table 5 Summary of baseline concomitant medications
- Table 6 Summary of important protocol deviations
- Table 7 Summary of exposure to randomized investigational product

11.2 Safety and Tolerability Analysis

11.2.1 Lists of Tables

Table 8 Permanent discontinuation of study regimen by treatment arm (a) during the oral phase, (b) during the injection phase, and (c) during the on-treatment

Table 9 Adverse experiences by MedDRA preferred term and severity (ordered by system organ class) (a) during the oral phase, (b) during the injection phase, (c) during the tail phase, and (d) during the on-treatment

Table 10 Adverse experiences by MedDRA preferred term and severity – including severe, potential life-threatening or fatal events only (a) during the oral phase, (b) during the injection phase, (c) during the tail phase, and (d) during the on-treatment

Table 11 Adverse experiences by MedDRA preferred term and relationship to study product (a) during the oral phase, (b) during the injection phase, (c) during the tail phase, and (d) during the on-treatment

Table 12 Elevation of liver chemistry and other lab test events (a) during the oral phase, (b) during the injection phase, (c) during the tail phase, and (d) during the on-treatment

Table 13 Summary of Injection Site Reaction Characteristics

Table 14 Summary of characteristics of common ISR symptoms

Table 15 Summary of change in laboratory test at follow up from baseline by visit and cohort

Table 16 Summary of ECG values by treatment arm and visit

Table 17 Summary of maximum change in corrected QTc intervals by category for change from baseline

Table 18 Listing of expedited adverse events (EAE) or serious adverse events (SAE) with the details of the events including severity, relationship to study product, time between onset and last injection, number of injections received (if the events occurring after the 1st injection), and a summary of the event

Table 19 Proportion of participants experiencing any Grade 2 or higher clinical AEs and laboratory abnormalities that occur (a) during the oral phase, (b) during the injection phase (c) during the tail phase, and (d) during the on-treatment period

Table 20 The proportion of participants who discontinue the study product for reasons of toxicity, tolerability, or acceptability (a) prior to completion of the full oral phase and (b) prior to completion of the full injection phase.

11.2.2 List of Figures

Figure 1 Kaplan-Meier curves of time to permanent discontinuation by treatment arm (For those who complete the study and currently stay in the study, their time to permanent discontinuation will be censored at the last visit date)

Figure 2 Kaplan-Meier curves of time to permanent discontinuation by treatment arm (For those who enter the injection phase and currently stay in the study, their time to permanent discontinuation will be censored at the last visit date)

Figure 3 Shift scatter plot of some laboratory measures at each visit week vs. baseline

Figure 4 Box plots of maximum some laboratory measures (AST, ALT, ALP, total bilirubin, CPK, Creatinine, Creatinine clearance) elevation from baseline by treatment arm and phase

Figure 5 Scatter plots of maximum liver chemistries (a) during the oral (b) during the injection (c) during the tail phase and (d) during the on-treatment phase vs. baseline.

Figure 6 Matrix plot of maximum of liver chemistries (a) during the oral (b) during the injection (c) during the tail phase and (d) during the on-treatment phase

Figure 7 Cumulative incidence plot of the time to first occurrence of grade 1 or greater elevation in ALT/AST will be generated by treatment arm (a) since the enrolment date and (b) since the first injection date

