8.2.2 Changes from the Baseline

For the variables that the changes from the baseline will be evaluated in the analyses, the changes will be calculated by subtracting the baselines values of the variables from the values at post-baseline visits. If the baseline or the post-baseline value is missing, then the change from the baseline will be missing.

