9.5.3 Local Laboratory Values

Scatter plots of some local laboratory values measured during the course of the study vs. the values at the baseline. If appropriate, horizontal/vertical lines representing boundaries for abnormal values will be plotted.

For each local laboratory measure, summary statistics will also be presented by treatment arm and visit time, as well as changes from baseline for post-enrollment values. Clinical laboratory abnormalities without an associated clinical diagnosis will also be reported as AEs and will be included in the tabulation of AEs described above.

In addition, the number (percentage) of participants with local laboratory values recorded as meeting Grade 1 AE criteria or above as specified in the DAIDS AE Grading Table (see Section 6.4.2 of the protocol) will be tabulated by treatment arm for each safety visit time point. In addition to SAEs, a list of the participants with the results: ALT \geq 3xULN and bilirubin \geq 2xULN will be provided.

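### Figure 4 plots the maximum elevation from baseline for creatinine clearance, where the adverse direction is a fall, so that one panel shows the most favourable value and can miss a transient decline

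*SAP*

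**What the plan says.** The figure list in SAP Section 11.2.2 opens the entry with "Figure 4 Box plots of maximum some laboratory measures". It then names the measures and the direction: "AST, ALT, ALP, total bilirubin, CPK, Creatinine, Creatinine clearance) elevation from baseline by treatment arm and phase". One statistic (the maximum) and one direction (elevation) cover all seven measures, and no exception is made for creatinine clearance.

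Section 8.2.2 fixes the sign of a change: "the changes will be calculated by subtracting the baselines values of the variables from the values at post-baseline visits". A fall in clearance is therefore a negative number.

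Other planned outputs bear on the same marker:
- Section 9.5.3: "For each local laboratory measure, summary statistics will also be presented by treatment arm and visit time, as well as changes from baseline".
- Section 9.5.3 also counts, by arm and safety visit, "participants with local laboratory values recorded as meeting Grade 1 AE criteria or above as specified in the DAIDS AE Grading Table".
- Section 11.2.1: "Table 15 Summary of change in laboratory test at follow up from baseline by visit and cohort". Table 19 in the same list gives the proportion of participants with Grade 2 or higher events, laboratory abnormalities included, by phase.
- Section 11.2.2: "Figure 3 Shift scatter plot of some laboratory measures at each visit week vs. baseline". The measures are not named.

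Section 12 says that figure shells are attached. They are not in the text at hand.

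**The concern.** A box plot of a per-participant extreme is meant to show how far each participant moved in the harmful direction during a phase. A maximum does that for AST, ALT, ALP, total bilirubin, CPK and serum creatinine. For creatinine clearance it does the reverse: the value kept is the best one, and a low value at one visit is discarded whenever any other visit is higher.

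It looks like a drafting slip. The liver box plots in Sections 9.5.4.2 and 10.2.2 cover only AST, ALT, ALP and bilirubin, for which upward is the right direction. Figure 4 takes the same form and adds CPK, creatinine and creatinine clearance without reversing the last. In the SAP text at hand this is the only place that names creatinine clearance, so the one explicit instruction for it points the wrong way. A reader could take the panel as renal reassurance that it cannot give.

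**Working it through.** The SAP states no figure on this point, so there is none to reproduce. The check applies its definition of change to the statistic in Figure 4 and then illustrates the size.

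**Step 1, direction.** For participant i with baseline B and post-baseline values Y(1) to Y(K), Section 8.2.2 gives change C(j) = Y(j) - B. Figure 4 plots max C(j) = max Y(j) - B. For clearance this is the highest, least adverse value. The largest fall is min C(j) = min Y(j) - B, which Figure 4 does not plot.

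**Step 2, number of visits.** Section 4.4 lists three visits after enrolment up to the first injection (Weeks 2, 4, 5), 10 visits from Week 6 to Week 41 in Cohort 1, 14 in Cohort 2, and six tail visits. The SAP does not say at which of these clearance is measured, so these are upper limits for K.

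**Step 3, one isolated fall.** Assume independent normal errors with the same SD at baseline and at each visit. The baseline error averages to zero, so the mean maximum change is SD × e(K), where e(K) is the expected maximum of K standard normals. A large fall at one visit almost removes that visit from the maximum, leaving about SD × e(K-1). With an assumed SD of 12 mL/min:

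| K | No fall: 12 × e(K) | One large fall: 12 × e(K-1) | Shift |
|---|---|---|---|
| 3 | 12 × 0.846 = 10.2 | 12 × 0.564 = 6.8 | 3.4 |
| 6 | 12 × 1.267 = 15.2 | 12 × 1.163 = 14.0 | 1.2 |
| 10 | 12 × 1.539 = 18.5 | 12 × 1.485 = 17.8 | 0.6 |
| 14 | 12 × 1.703 = 20.4 | 12 × 1.668 = 20.0 | 0.4 |

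A simulation on the same model (200,000 participants, baseline mean 110 mL/min, one fall of 40 mL/min) gives medians that agree. The maximum moves from +15.1 to +13.9 with six visits and from +18.8 to +18.3 with 11. The minimum moves from -15.1 to -40.2 and from -18.9 to -40.3.

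**Step 4, a sustained fall.** Median changes at SD 12 and six visits:

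| True pattern | Maximum change (as titled) | Minimum change |
|---|---|---|
| No fall | +15.1 | -15.1 |
| Sustained fall of 10 | +5.1 | -25.1 |
| Sustained fall of 20 | -4.9 | -35.1 |
| One fall of 40 | +13.9 | -40.2 |

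A sustained fall lowers the plotted maximum by its full size (15.1 - 5.1 = 10.0; 15.1 + 4.9 = 20.0), so the difference between arms survives. The level still misleads. Over SD 8 to 15 and six or 11 visits, a true sustained fall of 10 gives a median maximum of +0.1 to +13.7, and 50% to 79% of participants have a positive value.

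**Step 5, the creatinine panel.** If serum creatinine varies inversely with clearance, the isolated 40 mL/min fall gives a median maximum creatinine ratio to baseline of 1.57 (six visits) or 1.58 (11 visits). The creatinine panel of the same figure would show it.

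**The case against.** The strongest reply is that little is lost. Serum creatinine is plotted in its adverse direction in the same figure, and step 5 shows that it would pick up the fall that the clearance panel misses. Section 9.5.3 gives signed changes for every local laboratory measure by arm and visit, and graded counts as far as the grading table covers the measure. Grade 2 or higher laboratory abnormalities enter the primary safety endpoint (Section 9.5.5) and Table 19. The shells may already set the direction for clearance. All of this stands, and it limits the point to one panel. It does not correct that panel: by-visit summaries and counts do not show each participant's worst change in clearance by phase, which is the purpose of such a plot.

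A reader might infer more than the SAP supports, in three ways.
- *That renal decline is hidden in the analysis as a whole.* The outputs just listed, and the surviving arm difference in step 4, contradict this.
- *That Table 12 also counts elevations only.* Its title is "Table 12 Elevation of liver chemistry and other lab test events". The word for elevation may govern liver chemistry alone, with other laboratory events as a second item. An ambiguous title does not establish the claim.
- *That the panel would show improvement in nearly everyone.* Under the model of step 3 with no renal effect, the chance that at least one of K visits exceeds baseline is K/(K+1). That is 75% at three visits, 86% at six and 91% at 10. A sustained fall lowers it further.

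The illustration also depends on the visit count. With three visits, as in the oral phase, one large fall cuts the mean maximum by about a third (10.2 to 6.8), so it does register there. With the listed injection-phase and tail counts the shift is about 1 mL/min or less at SD 12.

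**Conclusion.** The point holds for the creatinine clearance panel of Figure 4 and no further. As titled, that panel displays the wrong extreme: an isolated fall in a phase with six or more measurements is almost invisible, while a sustained fall still shows as a difference between arms. The direction of the error follows from Sections 8.2.2 and 11.2.2 alone. The sizes rest on assumed SDs, visit counts, independent errors and fall patterns that the SAP does not give. The figure is descriptive, and no endpoint, test or decision rule uses it. Severity is minor, and the point lapses if the attached shell already reverses the direction for clearance.

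**What to change.** In Section 11.2.2, state that for creatinine clearance Figure 4 plots the maximum decrease from baseline (lowest post-baseline value in the phase minus baseline), and keep maximum elevation for the other six measures. Alternatively, retitle the figure as maximum change in the adverse direction and state that direction for each measure. Make the attached figure shell agree. Table 12 needs no change on this account. The cost is one line of SAP text and one programming change (minimum in place of maximum for one measure), with no new data.
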